#### 12.3 Guidelines for evaluation of measurable disease

All measurements should be taken and recorded in metric notation. The same method of assessment and the same technique should be used to characterize each identified and reported lesion at baseline and during follow-up.

#### 12.4 Response Criteria

##### 12.4.1 Evaluation of Target Lesions

## Memorial Sloan-Kettering Cancer Center IRB Protocol

**IRB#: 08-123 A(8)**

Complete Response (CR):	Disappearance of all target lesions
Partial Response (PR):	At least a 30% decrease in the sum of the LD of target lesions, taking as reference the baseline sum LD
Progressive Disease (PD):	At least a 20% increase in the sum of the LD of target lesions, taking as reference the smallest sum LD recorded since the treatment started or the appearance of one or more new lesions
Stable Disease (SD):	Neither sufficient shrinkage to qualify for PR nor sufficient increase to qualify for PD, taking as reference the smallest sum LD since the treatment started

### 12.4.2 Evaluation of Non-Target Lesions

Complete Response (CR):	Disappearance of all non-target lesions and normalization of tumor marker level
Incomplete Response/ Stable Disease (SD):	Persistence of one or more non-target lesion(s) or/and maintenance of tumor marker level above the normal limits
Progressive Disease (PD):	Appearance of one or more new lesions and/or unequivocal progression of existing non-target lesions (1)

### 12.4.3 Evaluation of Best Overall Response

The best overall response is the best response recorded from the start of the treatment until disease progression/recurrence (taking as reference for PD the smallest measurements recorded since the treatment started). In general, the patient's best response assignment will depend on the achievement of both measurement and confirmation criteria.

## Memorial Sloan-Kettering Cancer Center IRB Protocol

**IRB#: 08-123 A(8)**

Target lesions	Non-Target lesions	New Lesions	Overall response
CR	CR	No	CR
CR	Incomplete response/SD	No	PR
PR	Non-PD	No	PR
SD	Non-PD	No	SD
PD	Any	Yes or No	PD
Any	PD	Yes or No	PD
Any	Any	Yes	PD

### 12.4.4 Confirmation of Response

There will be no repeat imaging studies done solely for the purpose of confirming response. Patients will have follow-up imaging studies as outlined in the protocol and responses that are confirmed on follow-up scans will be noted.

### 12.4.5 Duration of Overall Response/ Progression Free Survival

The duration of overall response is measured from the time measurement criteria are met for CR or PR (whichever status is recorded first) until the first date that recurrence or PD is objectively documented, taking as reference for PD the smallest measurements recorded since the treatment started.

Progression Free Survival will be calculated from the start of treatment until progressive disease or death. Patients who die before documented progression will be considered failures at their time of death. If the patient did not progress or die, the patient will be censored on the date of last follow-up.

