### 10.0 EVALUATION DURING TREATMENT/INTERVENTION

**Table 7. Schedule of Events**

Procedure	Screening		Cycle 1			Additional Cycles (Years 1-4)		Additional Cycles (Years 5+)		Post Treatment/ Withdrawal 	Survival Follow-up
	≤ 30 Days Prior to Dosing	≤ 14 Days Prior to Dosing	Day 1 (± 3)	Day 14 (± 3)	Day 28 (± 3)	Day 1 (± 3)	Day 28 (± 3)	Day 1 (± 3)	Day 56 (± 3)		
Informed Consent		X									
Medical History		X									
Physical Examination, KPS		X	(X) 	X		X		X 		X	
Lab Studies											
Pregnancy Test 		X									
Hematology 		X	(X) 	X		X		X 		X	
Biochemistry 		X	(X) 	X		X		X 		X	
PT/PTT		X									
Fasting Lipids 		X	(X) 			X		X 		X	
HBV-DNA, HBsAg, HBs Ab, HBs Ab, HCV-RNA-PCR 	X										
HBV DNA, HCV RNA-PCR 			X			X		X		X	
Other Assessments											
12-lead EKG	X										
Pulmonary Function Tests	X										
Disease Assessment/Tumor measurements 	X						X 		X 	X	
Adverse Events 			X	X		X		X 		X	
Concomitant Medications		X	X	X		X		X 		X	
Treatment compliance 					X		X		X		
Everolimus 			X →	→	→	→	→	→	→		
Survival Status 											X
Tumor Tissue Evaluation 	X										

(X) – if applicable    X → - start and continue treatment    → - continue treatment

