## Memorial Sloan-Kettering Cancer Center IRB Protocol

IRB#: 08-123 A(8)

Footnotes for Schedule of Events	
1. Complete blood count (CBC) with differential and platelets	
2. Comprehensive panel (i.e. serum electrolytes including sodium, potassium, chloride, bicarbonate, phosphorus, calcium, glucose, blood urea nitrogen, creatinine, SGOT (AST), SGPT (ALT), alkaline phosphatase, total bilirubin, total protein, albumin, uric acid).	
Fasting Lipids include triglycerides, total cholesterol, HDL and LDL.	
3. Disease Assessment/Tumor Measurements: Re-staging imaging studies will be performed after every two cycles of treatment (1 cycle = 4 weeks) during the first five years of treatment and after study completion or withdrawal. Imaging studies should be performed during weeks 7 or 8. The same imaging studies performed at baseline (e.g., CT or MRI) should be performed throughout the study, when possible. Baseline chest CT or chest x-ray must be performed. If chest CT or chest x-ray is not part of the disease assessment, it must be repeated every 2 months. Bone x-ray(s)/scan to be performed if bone metastases are present.	
4. Adverse Events: Patients must be followed for adverse events from the first day of study treatment until at least 28 days after the last on-study treatment administration, or until all serious or study drug-related toxicities have resolved or are determined to be "chronic" or "stable," whichever is later. Serious adverse events should be monitored and reported as described in the protocol.	
5. Post-study survival status: Follow-up survival information will be collected for all patients by clinic visit or telephone contact approximately every 6 months for up to 2 years from the date of first dose of Everolimus. Patients will be followed until disease progression and/or death.	
6. Physical Examination/Hematology/Biochemistry/Fasting Lipids: Physical Examination/ Hematology/ Biochemistry/Fasting Lipids on Cycle 1 Day 1 is not required if performed within 7 days of Day 1 unless clinically indicated.	
7. Post Treatment/Withdrawal: This visit will take place 1 month after the last dose of study drug. Patients with ongoing study drug-related toxicities should be followed as dictated in footnote 4. These patients should be followed at the interval deemed appropriate by their study physician.	

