#### 12.2 Definitions

Measurable lesions: lesions that can be accurately measured in at least one dimension with longest diameter  $\geq$  20 mm using conventional techniques or  $\geq$  10 mm with spiral CT scan.

Non-measurable lesions: all other lesions (or sites of disease) including small lesions (longest diameter  $<$  20 mm with conventional techniques or  $<$  10 mm using spiral CT scan) are considered non-measurable disease. Bone lesions, leptomeningeal disease, ascites, pleural/pericardial effusions, lymphangitis cutis/pulmonis, inflammatory breast disease, abdominal masses (not followed by CT or MRI), and cystic lesions are all non-measurable.

Target lesions: all measurable lesions – up to a maximum of five lesions per organ and 10 lesions in total, representative of all involved organs – should be identified as target lesions and recorded and measured at baseline. Target lesions should be selected on the basis of their size (lesions with the longest diameter) and their suitability for accurate repeated measurements (either by imaging techniques or clinically). A sum of the longest diameter (LD) for all target lesions will be calculated and reported as the baseline sum LD. The baseline sum LD will be used as reference by which to characterize the objective tumor response.

Non-target lesions: all other lesions (or sites of disease) should be identified as *non-target lesions* and should also be recorded at baseline. Measurements of these lesions are not required, but the presence or absence of each should be noted throughout follow-up.

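### Minor: Section 12.4.5 censors PFS at an undefined last follow-up date instead of the last tumor assessment, so unassessed time can count as progression-free

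*Combined protocol and SAP*

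**What the plan says.** Section 12.4.5 measures PFS from start of treatment to progression or death, and counts a death without documented progression as an event on the date of death. For everyone else the rule is: "If the patient did not progress or die, the patient will be censored on the date of last follow-up". The term is not defined anywhere.

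The protocol uses the word follow-up in two ways.

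- **Lesion assessment, in Section 12.** Section 12.2 says of non-target lesions that "the presence or absence of each should be noted throughout follow-up". Section 12.3 asks for the same technique "to characterize each identified and reported lesion at baseline and during follow-up". Section 12.4.4 says "Patients will have follow-up imaging studies as outlined in the protocol and responses that are confirmed on follow-up scans will be noted".
- **Survival contact, in Section 10.0.** The Schedule of Events has a column headed "Survival Follow-up", and footnote 5 explains it: "Follow-up survival information will be collected for all patients by clinic visit or telephone contact approximately every 6 months for up to 2 years", counted from the first dose.

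Footnote 3 sets re-staging every two cycles "during the first five years of treatment and after study completion or withdrawal". The table marks a tumor assessment at the post-treatment/withdrawal visit, one month after the last dose. In the survival column it marks neither a tumor assessment nor a physical examination. Footnote 5 adds: "Patients will be followed until disease progression and/or death". It gives no method or interval for detecting progression after that visit.

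Sections 2.0 and 12.1 make RECIST the basis for PFS and progression. In Section 14.0 the primary endpoint is the binary proportion progression-free at two months. PFS as a time enters through a log rank test against marker categories.

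**The concern.** Take a patient who stops treatment for toxicity or by choice, has a clean withdrawal scan, and is alive at a survival call a year later. Under one reading of Section 12.4.5 that patient is censored at the scan; under the other, at the call. In the second case the months between them enter the risk set as progression-free although nobody was scheduled to look for progression.

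Two analysts could each follow the sentence and report different curves. The looser reading errs in one direction only, in favor of the drug. At stake are any time-to-event PFS estimate and the marker log rank test, which would compare small groups.

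**Working it through.** **1. The plan's own figures.** Section 14.0 gives 23 patients in stage 1, continuation at 13 or more progression-free, 37 in total, and success at 24 or more. With X1 ~ Bin(23, p) and X2 ~ Bin(14, p):

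- P(early stop) = P(X1 ≤ 12)
- P(positive) = Σ over x = 13 to 23 of P(X1 = x) · P(X2 ≥ 24 − x)

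| Quantity | Plan | Exact |
|---|---|---|
| P(positive), p = 0.50 | 0.05 | 0.0482 |
| P(positive), p = 0.70 | 0.80 | 0.8011 |
| P(early stop), p = 0.50 | 66% | 66.1% |

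All reproduce. No censoring date appears in these formulas, so the sentence does not affect them, provided every evaluable patient has a two-month scan.

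**2. Direction.** The Kaplan-Meier estimate is S(t) = Π(1 − d_j/n_j). Moving a censoring date later leaves every d_j unchanged and can only increase n_j. Each factor therefore stays the same or rises.

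**3. Size, by simulation.** The documents give no dropout rate, so the sizes rest on assumptions.

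- Median PFS 2 to 3 months (Sections 3.2 and 14.0); central 2.5, exponential.
- Post-progression survival 4 to 6 months, from the 6 to 9 month survival in Section 3.2 (6 − 2 = 4; 9 − 3 = 6); central 4.5, exponential.
- Leaving treatment without progression at 0.02, 0.04 or 0.08 per month (assumed), which puts 4% to 22% of patients off treatment without documented progression; central 10%.
- Scans every 56 days plus one a month after stopping; contacts every 6 months to month 24 (Section 10.0).
- Uniform accrual over 15 months, the middle of the stated 10 to 20.

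The central scenario used 600,000 patients, with data cut 24 months after last entry. The benchmark is the same scan grid without dropout.

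| Censoring rule | 6-month PFS | 12-month PFS |
|---|---|---|
| Last contact | 24.39% | 7.77% |
| Last scan, deaths kept as events | 24.06% | 7.07% |
| Last scan, late deaths also censored | 20.76% | 4.02% |
| Benchmark | 21.6% | 4.6% |

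The difference between the first two rows is 0.33 points at 6 months and 0.70 at 12. Over all scenarios it is 0.1 to 1.2 points at 6 months and 0.2 to 2.6 at 12. The median is 3.68 months under both rules. A separately coded run on the same inputs gave 24.3% and 24.0% at 6 months.

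**4. At the trial's size** (n = 37, 4,000 simulated trials, same cut). The share of patients whose date moves is 1.1%, and 0.011 × 37 ≈ 0.4 per trial. At least one date moves in 34.5% of trials. The 6-month shift averages 0.35 points, has a 90th percentile of 1.7, and is never negative. The median changes in 0.7% of trials.

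**5. Early cut** (3 months after last entry; no such cut is stated). If deaths are known at once: 23.91% against 21.88%, or 2.0 points. If known only at the next contact: 23.98% against 21.19%, or 2.8 points.

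**6. Marker log rank test.** Applying the p-S6 shares in Table 2 to 37 patients gives 45/85 × 37 ≈ 20, and about 9 each for grades 1+/2+ and 3+; groups of 20, 9 and 8 were used. With no marker effect and the 24-month cut, rejection is 6.8% (last contact) against 6.1% (last scan), and significance changes in 1.5% of 2,000 trials. If one group of 8 leaves at 0.20 per month and the others at 0.02, the figures are 10.2%, 9.2% and 3.1%.

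**The case against.** **The imaging reading is the more natural one.** Section 12 uses the word mostly for lesion assessment, including in the subsection just before the rule. This stands, and many analysts would censor at the last scan unprompted. But nothing requires it, and the schedule attaches the word to survival contact.

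**RECIST progression does not always need a scan.** Section 12.2 allows clinical measurement, Section 8.1 records palpable lesions, and survival contacts may be visits. This is a fair correction. However, no examination is marked in the survival column. It is a reason to write *tumor assessment* rather than *scan*.

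**Footnote 5 intends follow-up to progression.** If half of later progressions are picked up at contacts without a scan, the mature 6-month difference falls to 0.2 points (22.81% against 22.63%). If all are, it is 0.0 (21.27% against 21.25%). This stands as a limit on the size.

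**Little planned output is affected.** Section 14.0 names no Kaplan-Meier curve, median or 6-month estimate; only the marker test uses PFS time. True, and the main reason the point is minor.

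**The fix removes little bias.** In the central scenario it takes 6-month PFS from 24.4% to 24.1% against a benchmark of 21.6%, about 0.3 of 2.8 points. Most of the rest comes from unseen progressions counted only at death. With an early cut and all progressions captured at contacts, last-scan censoring is further from the benchmark (about 19.5% against 20.8%). Both facts stand. The second is why the sentence should also say that progression is counted by RECIST.

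**Other assumptions give larger effects.** A simulation with 10% to 30% of patients assigned a non-progression stop at 0.5 to 4 months shows about 2 to 7 points at 6 months (for example 32.8% to 26.1%). Its last-scan rule also censors deaths after the scan. That is a larger change than the one proposed here, since Section 12.4.5 counts such deaths as events.

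**Conclusion.** The concern holds, as a minor point. The wording lets a survival contact set the PFS censoring date, although no tumor assessment is scheduled after the withdrawal visit. The direction of the error is certain: the curve can only rise. Confidence in the undefined date is high. The sizes depend on the assumed dropout, survival and data cut: 0.1 to 1.2 points at 6 months once follow-up is mature, 2.0 to 2.8 points in the central scenario at an early cut, and almost no effect on the median.

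The primary decision is untouched. How to count an evaluable patient without a two-month scan is a separate gap in Section 14.0, which a censoring rule does not settle.

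**What to change.** In Section 12.4.5, replace the censoring date with the date of the last evaluable tumor assessment, or the start of treatment if there is none. State that progression is counted by RECIST, and keep death as an event.

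Optionally, add a sensitivity analysis. It would censor at the last scan any death that occurs two or more of that patient's own imaging intervals later. The interval is two cycles in the first five years and the one chosen under footnote 14 after that. Read the result as a lower bracket, not a better estimate: in the central scenario it gives 20.8% at 6 months, and with the 24.1% from last-scan censoring it spans the 21.6% benchmark.

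The cost is one sentence. Scan dates are already collected, and sample size, visits and the two-stage rule do not change. Reported PFS may be slightly shorter.

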## 13.0 CRITERIA FOR REMOVAL FROM STUDY

In the absence of treatment delays due to adverse event(s), treatment may continue until one of the following criteria applies:

- Completion of treatment per protocol
- Disease progression
- Intercurrent illness that prevents further administration of treatment
- Unacceptable adverse event(s)
- Patient decides to withdraw from the study, or

## Memorial Sloan-Kettering Cancer Center IRB Protocol

**IRB#: 08-123 A(8)**

- General or specific changes in the patient's condition render the patient unacceptable for further treatment in the judgment of the investigator
- Inability of subject to comply with study requirements

If at anytime, the patient is found to be ineligible for the protocol as designated in the inclusion and exclusion criteria detailed in Section 6.0 (i.e., a change in diagnosis), the patient will be removed from the study.

### 14.0 BIOSTATISTICS

The purpose of this study is to assess the efficacy of Everolimus in patients with progressive urothelial cancer who have received prior cytotoxic chemotherapy. Historically, patients in this setting experience a median time to progression of 2-3 months (as illustrated in Section 3.1). Thus, the primary endpoint of this study will be the proportion of patients who are progression-free after two months on-study.

The sample size and stopping rules will be determined according to Simon's Minimax two-stage design. A two-month progression free survival rate of 50% would be considered not promising, while a 70% two-month PFS rate would be considered promising. In Stage 1 of the trial, 23 evaluable patients will be accrued to the study. If twelve or more patients demonstrate progression on imaging after two months on-study, the study will be terminated early and declared to have a negative result. If 13 or more patients are progression-free at two months, enrollment will be extended to accrue a total of 37 patients. If 24 or more patients are progression-free after their two-month scan (i.e. after Stage 2), the treatment will be declared effective and worthy of further testing.

**Patients will be considered inevaluable for the primary objective (PFS at 2 months) if they receive ≤one cycle of protocol therapy and are discontinued from protocol treatment for either rapid clinical deterioration related to progression of disease or adverse events unrelated to Everolimus. Patients with still be evaluable for toxicity assessment.**

For the purposes of this study, the Type I (false acceptance of a non-promising therapy) and Type II (false rejection of a promising therapy) error rates have been set at 0.05 and 0.20, respectively. This statistical design would effectively discriminate between two-month PFS rates of <50% and >70% and yields 80% probability of a positive result if the true two-month PFS rate is >70%. It yields 95% probability of a negative result if the true two-month PFS rate is <50%. The probability of early stopping under the null hypothesis is 66%.

The secondary endpoint of response rate will be estimated as the proportion of patients meeting the criteria outlined in Section 3.4.2.3 for a complete response or partial response. This proportion will be reported along with its binomial confidence interval.

An accrual rate of 2-4 patients per month is anticipated, and thus the expected accrual time for the study will be approximately 10-20 months.

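### The Stage 1 stopping rule is off by one: 12 progression-free of 23 meets neither the stop nor the continue rule, and the stated 66% early stopping fits only a stop at 12 or fewer

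*Combined protocol and SAP*

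**What the plan says.** Section 14.0 names the design: "The sample size and stopping rules will be determined according to Simon's Minimax two-stage design". It sets the rates: "A two-month progression free survival rate of 50% would be considered not promising, while a 70% two-month PFS rate would be considered promising". The error limits are 0.05 (Type I) and 0.20 (Type II).

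The decision rules follow in the same section:

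- Stage 1 size: "In Stage 1 of the trial, 23 evaluable patients will be accrued to the study".
- Stop: "If twelve or more patients demonstrate progression on imaging after two months on-study, the study will be terminated early".
- Continue: "If 13 or more patients are progression-free at two months, enrollment will be extended to accrue a total of 37 patients".
- Final success: "If 24 or more patients are progression-free after their two-month scan (i.e. after Stage 2), the treatment will be declared effective".

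The section then reports an operating characteristic, in percent: "The probability of early stopping under the null hypothesis is 66".

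Section 12.4.5 defines PFS failure more broadly than the stop rule does: "Patients who die before documented progression will be considered failures at their time of death".

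**The concern.** The stop rule counts progressions and the continue rule counts patients who are progression-free. With 23 patients the two should be complements, and they are not. Twelve or more progressed is the same as 11 or fewer progression-free; the other branch starts at 13. The outcome of 12 progression-free and 11 progressed falls between them, and no other section assigns it.

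This is the trial's only futility decision. At a true rate of 50%, 11 and 12 progression-free are the two most likely Stage 1 results, so the gap sits where the rule is most often needed. At 12 of 23 the printed text neither ends the trial nor authorises enrolment beyond 23. If that result were taken as a reason to continue, 14 more patients would be treated with little prospect of a positive result, and early stopping under the null would fall below the stated figure.

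There is a smaller mismatch in the same sentence. The stop count is limited to progression seen on imaging, whereas Section 12.4.5 treats death before documented progression as a failure. An evaluable patient who dies before the scan is a PFS failure but is not in the stop count.

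**Working it through.** **Inputs, all from Section 14.0.** Null rate p0 = 0.50, target rate p1 = 0.70, Stage 1 size n1 = 23, total n = 37 (so 14 in Stage 2), success at 24 or more of 37, error limits 0.05 and 0.20, stated early stopping under the null 66%.

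**Assumption for the figures below.** Each evaluable patient is either progression-free at two months or has progressed on imaging.

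**Formulas.** Let X1 ~ Binomial(23, p) be the number progression-free in Stage 1, X2 ~ Binomial(14, p) the number in Stage 2, and r1 the largest Stage 1 count that stops the trial.

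- Early stopping: PET = P(X1 ≤ r1).
- P(declare effective) = Σ over x1 > r1 of P(X1 = x1) × P(X2 ≥ 24 − x1).
- Expected sample size: EN = 23 + 14 × (1 − PET).

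**Step 1. Reproduce the stated 66%.** Success is held at 24 of 37:

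| Stop if progression-free ≤ | PET at 50% | Type I error | Power at 70% | EN at 50% |
|---|---|---|---|---|
| 10 | 0.3388 | 0.0494 | 0.8071 | 32.26 |
| 11 (printed stop rule, 12 of 23 continues) | 0.5000 | 0.0493 | 0.8064 | 30.00 |
| 12 | 0.6612 | 0.0482 | 0.8011 | 27.74 |
| 13 | 0.7976 | 0.0443 | 0.7778 | 25.83 |

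Only a stop at 12 or fewer gives 66%. It also meets both error limits.

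**Step 2. Check the continue rule.** P(X1 ≥ 13) at 50% is 0.3388 = 1 − 0.6612. The continue rule therefore agrees with the 66%; the stop rule does not.

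**Step 3. Check the named design.** An exhaustive search for the minimax design at p0 = 0.50, p1 = 0.70 and error limits 0.05 and 0.20 returns a stop at 12 or fewer of 23 and failure at 23 or fewer of 37. That matches n1, n, the continue rule, the success rule and the 66%. The stop sentence is the only element that differs.

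**Step 4. Size of the gap.**

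- P(X1 = 12) at 50% = 0.1612, and 0.5000 + 0.1612 = 0.6612, which accounts for the whole discrepancy. P(X1 = 11) is also 0.1612.
- P(X1 = 12) at 70% = 0.0332.

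**Step 5. If 12 of 23 were read as continue.** Success would then need 24 − 12 = 12 or more of the next 14.

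- At 50%: P(X2 ≥ 12) = 0.0065.
- At 70%: P(X2 ≥ 12) = 0.1608.
- Added Type I error: 0.1612 × 0.0065 ≈ 0.0010, taking 0.0482 to about 0.0493 (the sum before rounding).
- Added power: 0.0332 × 0.1608 ≈ 0.0053, taking 0.8011 to 0.8064.
- Expected sample size under the null: 23 + 14 × 0.5000 = 30.0, against 23 + 14 × 0.3388 = 27.7.

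**Step 6. Relax the imaging assumption.** If some failures are deaths before the scan, the printed stop rule triggers less often than 50.0% and more outcomes are unassigned. For example, 11 progression-free, 11 progressed on imaging and 1 death meets neither rule, and nor does 10, 11 and 2. The gap widens.

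**The case against.** The best defence is that the plan can be repaired from its own contents. The named minimax design, the two rates, the error limits, both sample sizes, the success rule and the 66% together fix the Stage 1 cut-off at 12, and enrolment past 23 is authorised only at 13 or more progression-free. On that view a reader can settle 12 of 23 before any data are seen, and this is one miswritten clause among several consistent ones. The worse consequences (14 further patients, 50% early stopping, expected sample size 30.0) follow only if 12 of 23 is read as continue, which the continue rule does not support. Even then the Type I error is 0.049 and power 0.806, both within limits.

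Most of this stands. The error rates are not the problem, and the intended cut-off can be recovered. But recovering it takes a calculation and means overriding the printed stop sentence, which sets termination at 12 progressions rather than 11. A stopping rule should not need that.

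Two lesser points also have weight. The imaging mismatch is secondary: some early failures are already classed as inevaluable in Section 14.0, and a death never counts as a success under the continue or final rules. And the text is amendment A(8), dated 03/04/15, with provisions for patients past five years of treatment and an expected accrual of 10–20 months, so the Stage 1 decision may already have been taken. The documents do not say.

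**Conclusion.** The concern holds. The stop sentence in Section 14.0 is wrong as written: it leaves 12 of 23 progression-free without an action and conflicts with the continue rule, the stated 66% and the named design, all of which require a stop at 12 or fewer. The unassigned result has probability 16.1% at a true rate of 50% and 3.3% at 70%, and the printed stop rule gives early stopping of 50.0% under the null. These figures assume that every evaluable failure is progression on imaging; without that assumption the gap is larger.

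The effect on Type I error and power is negligible, and the 24-of-37 success rule is unaffected. The point must be fixed because it concerns the trial's only futility decision and a stated operating characteristic that the printed stop rule does not deliver, not because error is inflated.

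**What to change.** Replace the stop and continue sentences in Section 14.0 with one statement in progression-free counts:

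> Stop if 12 or fewer of the 23 evaluable Stage 1 patients are progression-free at two months (that is, 11 or more are not); continue to 37 if 13 or more are. Among evaluable patients, death before the two-month scan counts as not progression-free.

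This removes the restriction to imaging from the stop count, brings it into line with Section 12.4.5 and makes the stated 66% correct. If the Stage 1 decision has already been made, also record which cut-off was applied and the observed count.

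The cost is a one-sentence amendment. Sample size, error limits, success rule and the inevaluability clause do not change. How inevaluable or unassessed patients are handled is a separate matter that this wording does not settle.

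### An evaluable patient who stops in weeks 5 to 8 for clinical deterioration and has no two-month scan is not counted as a failure, and Sections 12.4.5 and 14.0 conflict on whether that patient counts as progression-free.

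*Combined protocol and SAP*

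**What the plan says.** Section 14.0 makes the primary endpoint the proportion progression-free after two months and tests it in a Simon minimax design: "A two-month progression free survival rate of 50% would be considered not promising, while a 70% two-month PFS rate would be considered promising". Its counting rules are worded in three ways.

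- Stage 1 stop: "If twelve or more patients demonstrate progression on imaging after two months on-study, the study will be terminated early".
- Stage 1 continuation: "If 13 or more patients are progression-free at two months, enrollment will be extended to accrue a total of 37 patients".
- Final success: "If 24 or more patients are progression-free after their two-month scan".

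Section 14.0 treats rapid deterioration from the cancer as a reason for being inevaluable, but only for patients who received one cycle or less. It has no rule for deterioration after that.

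Sections 12.4.1 to 12.4.3 define progression by target lesions, non-target lesions and new lesions. Section 12.4.5 adds death: "Patients who die before documented progression will be considered failures at their time of death". A patient with neither event is censored at last follow-up, not at the last tumor assessment.

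Section 13.0 lists disease progression as one reason for removal and, as a separate item, "General or specific changes in the patient's condition render the patient unacceptable for further treatment in the judgment of the investigator".

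In the Section 10.0 schedule of events, footnote 3 places the restaging scan in weeks 7 or 8 and also calls for imaging after withdrawal. Footnote 7 sets the withdrawal visit one month after the last dose. Footnote 5 continues survival follow-up for up to two years.

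**The concern.** Take a patient who completes cycle 1, is removed in week 6 as too ill to continue, and has no scan then or at two months. The patient is evaluable. If death comes in week 12, Section 12.4.5 dates the failure at week 12, so there is no event at two months. If the patient is alive at last contact after week 8, the patient is censored and again has no event at two months. Either way, no progression on imaging has been shown, so the Stage 1 stop does not count this patient.

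The sickest patients are the least likely to come back for a scan. Any credit given to them pushes the two-month rate upward, toward extending enrollment and declaring the drug effective. The thresholds have no slack: one such patient turns 12 of 23 into 13 of 23, or 23 of 37 into 24 of 37.

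The same patients enter the log-rank comparison of marker groups as late deaths or as censored observations. The documents give no basis for a direction or size of bias there.

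**Working it through.** **Inputs from Section 14.0.** Null rate 0.50 and alternative 0.70; "error rates have been set at 0.05 and 0.20, respectively"; 23 patients in Stage 1 and 37 in total; continue at 13 or more of 23; success at 24 or more of 37; stated early stopping under the null 66%.

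**1. Reproduce the design.** With X1 ~ Bin(23, p) and X2 ~ Bin(14, p):

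- P(early stop) = P(X1 ≤ 12)
- P(declared effective) = Σ over k = 13 to 23 of P(X1 = k) × P(X2 ≥ 24 − k)

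At p = 0.50, early stopping is 0.661 and the false-positive rate is 0.048. At p = 0.70, power is 0.801. A full minimax search returns the same design. The stated 66% therefore belongs to the gate at 12 or fewer progression-free. The wording with twelve or more progressions means 11 or fewer progression-free (23 − 12 = 11), for which early stopping is 0.50.

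**2. Timing.** The gap concerns patients who stop in weeks 5 to 8. A withdrawal visit one month later falls at about weeks 9 to 12. Even a completed withdrawal scan can therefore date progression after the two-month mark, and a patient removed in week 5 or 6 may never have the week 7-8 scan.

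**3. One Stage 1 result.** Suppose that 12 patients are scanned and progression-free, 10 have progression on imaging, and 1 stopped for deterioration unscanned (12 + 10 + 1 = 23). The stop count is 10, below twelve. The progression-free count is 13 if the unscanned patient is credited, so enrollment is extended. It is 12 if not, which stops the trial under the gate that gives 66%. The decision turns on a point that the plan does not settle.

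**4. If these patients are credited.** Let d be the share of all patients who are true two-month failures but are scored progression-free. The documents do not give d, so it is an assumption. At a true rate of 50% the observed rate is 0.50 + d, and d / 0.50 is the share of true failures missed.

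| d | Expected among 37 (37 × d) | Share of failures missed | Observed rate | False-positive rate | Early stopping |
|---|---|---|---|---|---|
| 0 | 0 | 0 | 0.500 | 0.048 | 0.661 |
| 0.01 | 0.4 | 2% | 0.510 | 0.062 | 0.625 |
| 0.025 | 0.9 | 5% | 0.525 | 0.087 | 0.569 |
| 0.05 | 1.9 | 10% | 0.550 | 0.146 | 0.472 |
| 0.10 | 3.7 | 20% | 0.600 | 0.329 | 0.287 |

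**5. If they are not credited at the final count.** The final count then cannot exceed the number truly progression-free. Even if Stage 1 never stopped the trial, the false-positive rate at a true 50% is at most P(Bin(37, 0.50) ≥ 24) = 0.049.

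**The case against.** The strongest reply is that the final rule counts patients who are progression-free after a two-month scan, and an unscanned patient does not meet those words. On that reading the false-positive rate stays at or below 4.9%, and no inflation figure applies. This stands, and it is why the figures in step 4 are conditional.

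Second, being absent from the stop count does not make a patient one of the 13 needed to continue. That is correct. But the continuation rule mentions no scan, so the text does not exclude such a patient either, and Section 12.4.5 gives no event by two months.

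Third, the plan schedules imaging at withdrawal. It does, and this will catch some cases. The visit is a month after the last dose, however, so for these patients it can fall after week 8, and nothing says how a missed or late scan is scored.

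Fourth, the rate is assumed. Entry at Karnofsky 60% or above, median progression-free survival of 2-3 months and median survival of 6-9 months make some cases plausible. They do not show how many patients stop in weeks 5 to 8, miss the scan and live past week 8.

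Fifth, making investigator-judged deterioration a PFS event would depart from PFS as determined by RECIST, which is the stated objective. This also stands, and it argues for a remedy that keeps the RECIST definition.

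**Conclusion.** The gap is real. By the stated rules, an evaluable patient who stops in weeks 5 to 8 for deterioration and has no two-month scan is not a failure, and the imaging-based stop omits this patient. Whether the patient is a success is unsettled: Section 12.4.5 allows it and the final-count wording in Section 14.0 argues against it.

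A reader might infer that the plan scores these patients as successes and that its true false-positive rate is therefore 9% to 15%. The documents do not support that. The figures of 8.7% to 14.6%, with early stopping of 57% to 47%, need both the crediting reading and an assumed 2.5% to 5% of all patients. If these patients are not credited at the final count, the false-positive rate is at most 4.9%.

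What holds without assumption is that the passages conflict on the primary endpoint, that one patient can change the decision at either stage, and that any credit given favors the drug. This should be corrected. It does not invalidate the design, whose stated properties reproduce.

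**What to change.** In Section 14.0, state that an evaluable patient counts as progression-free at two months only if alive with a two-month tumor assessment showing no RECIST progression. All other evaluable patients count as not progression-free: those with imaging progression, those who have died, and those who stopped for deterioration without such an assessment.

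Use this definition at both stages in place of the imaging-only wording. Stop if 12 or fewer of 23 are progression-free, which matches the stated 66%, and declare success at 24 or more of 37. This also gives every Stage 1 result an assigned action.

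For PFS as a time to event, keep RECIST progression or death as the main definition in Section 12.4.5. Add a sensitivity analysis that counts removal for cancer-related deterioration as an event on the date of removal. Section 9.3.5 already requires the reason for stopping to be recorded, so no new data are needed.

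The cost is a few sentences and one extra analysis. A patient who misses the two-month scan for an unrelated reason also counts as a failure, so the two-month rate may look slightly less favorable.
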